10.6 COVID-19 Management

The ongoing COVID-19 pandemic may impact the conduct of this clinical study. Therefore, the study Sponsor will continuously monitor and evaluate the development of the COVID-19 pandemic in the area of the study sites.

The safety of the subject has highest priority. The study Sponsor will modify the study conduct accordingly, if any potential safety issues arise. These decisions may include halting trial recruitment or the change of subject monitoring during the study. In all cases, the subject and/or the legal representative(s) will be informed.

To protect the subject's safety, welfare, and rights, the study Sponsor will continuously evaluate specific circumstances, such as the ability to conduct appropriate safety monitoring or the potential impact on the IMP supply chain.

Depending on the local situation, subjects may not be able to come to the site for protocol-specified visits. Therefore, existing processes will be modified or new processes will be implemented. Such modifications include, but are not limited to, alternative methods of safety assessments (e.g. switching in-person visits to phone calls or virtual visits, or alternative location for assessment, including local labs) or employ mobile teams to collect serum samples. In all cases, the subject and/or the legal representative(s) will be informed.

To mitigate risks to the subjects or in response to local governmental recommendations further recruitment can be temporarily halted or some assessments will be delayed. All alternative processes will be consistent with the protocol to the extent possible.

Changes in study visit schedules, missed visits or subject discontinuations due to COVID-19 will be recorded. In addition, the reason for the implementation of any contingency measures will be documented.

Moreover, the Sponsor will communicate any measures or modifications of the study protocol to the relevant CA and IRB in line with local requirements.

The COVID-19 measures are based on the FDA Guidance on Conduct of Clinical Trials of Medical Products during COVID-19 Public Health Emergency (as of 02-July-2020) and will be adjusted, if needed.

11. STUDY PURPOSE AND OBJECTIVES

11.1 Study Purpose

The purpose of the study is to demonstrate Lot-to-Lot manufacturing consistency of the final dose of the live-attenuated CHIKV vaccine candidate (VLA1553) in a healthy CHIKV-naïve population aged 18 to 45 years.

The outcome shall provide the basis for licensure of the vaccine.

11.2 Primary Objective

The primary objective is to demonstrate Lot-to-Lot manufacturing consistency of a live-attenuated CHIKV vaccine candidate (VLA1553) in terms of GMT 28 days following vaccination in a healthy population aged 18 to 45 years after a single immunization.

11.3 Secondary Objective

The secondary objective is to evaluate immunogenicity and safety of VLA1553 up to 180 days following vaccination in a healthy population aged 18 to 45 years after a single immunization.

12. STUDY DESIGN

12.1 Overall Study Design

This is a prospective, randomized, double-blinded, multicenter Phase 3 clinical study investigating three Lots of VLA1553 at the final dose (target 1x 10E4 TCID₅₀ per 0.5 mL). Overall, approximately 402 subjects will be enrolled (i.e. ICF signed) into the study, approximately 134 subjects per VLA1553 Lot (**Table 3**).

Subjects will be block-randomized in a 1:1:1 ratio into the three study arms to receive either of three Lots of VLA1553 as a single i.m. vaccination on Day 1 (Visit 1).

All subjects will be asked to return to the study site at Day 8 (Visit 2), Day 29 (Visit 3), Day 85 (Visit 4) and Month 6 (Day 180, Visit 5) for immunogenicity sampling. Safety data collection will capture solicited AEs until Day 11 and unsolicited AEs up to Day 180 (Month 6, Visit 5) from all subjects. AESIs will be captured 2 to 21 days post-vaccination. Subjects presenting with acute arthralgia within this time period will be followed-up until resolution and monitored for recurrences until the end of the study. SAEs will also be assessed until the end of the study (Month 6, Visit 5).

Table 2 below illustrates the subject distribution scheme.

Table 3. Subject Distribution

Study Arms	Vaccine	Cohort	Number of subjects (n)	Target Dose (TCID ₅₀ /dose)	Injection Volume (mL)
1	VLA1553	Lot 1	134	1x 10E4 TCID ₅₀ per 0.5 mL	0.5
2	VLA1553	Lot 2	134		0.5
3	VLA1553	Lot 3	134		0.5
Total N:					402

The clinical study design is displayed in the **Figure 1** below.

[figure not shown]

Figure 1. Study Design Lot-to-Lot Consistency Study VLA1553-302

12.2 Study Duration

The overall duration of the study is estimated to be approximately 8 months from study initiation (first subject enrolled) to study completion (last subject last visit).

The individual subject participation is approximately 7 months from enrollment to study completion unless prematurely discontinued.

12.3 Study Endpoints

12.3.1 Primary Endpoint

Immunogenicity

The primary endpoint is the Geometric mean titer (GMT) of CHIKV-specific neutralizing antibodies as determined by μ PRNT assay on Day 29 post-vaccination in subjects who tested negative for CHIKV antibodies at baseline.

12.3.2 Secondary Endpoints

Immunogenicity

The following secondary immunogenicity endpoints will be evaluated:

- Immune response as measured by CHIKV-specific neutralizing antibody titers on Day 8, Day 85 and Month 6 post-vaccination as determined by μ PRNT assay;
- Proportion of subjects with seroprotective levels (defined as [REDACTED] for baseline negative subjects) at Days 8, 29, 85 and Month 6 post-vaccination by μ PRNT assay;
- Proportion of subjects with seroconversion at Day 29 and Month 6 as determined by μ PRNT assay (seroconversion defined as CHIKV-specific neutralizing antibody titer of [REDACTED] for baseline negative subjects and [REDACTED] for baseline positive subjects);
- Fold increase of CHIKV-specific neutralizing antibody titers determined by μ PRNT assay at Days 8, 29, 85 and Month 6 post-vaccination as compared to baseline;
- Proportion of subjects reaching an at least 4-fold, 8-fold, 16-fold or 64-fold increase in CHIKV-specific neutralizing antibody titer compared to baseline as measured by μ PRNT assay.

Safety:

- Frequency and severity of solicited injection site and systemic reactions within 10 days post-vaccination;
- Frequency and severity of unsolicited adverse events (AEs) within 28 days post-vaccination;
- Frequency and severity of any AE during the entire study period;
- Frequency and severity of any serious adverse event (SAE) during the entire study period;
- Frequency and severity of any adverse event of special interest (AESI) within 2 to 21 days post-vaccination.

12.4 Randomization and Blinding

The approximately 402 subjects will be block-randomized into the three study arms in a ratio of 1:1:1 at Visit 1 as described in Section 12.1.

In order to minimize/avoid bias, assignment into one of these study arms will be blinded for these subjects and the site staff, as well as the biostatistician (i.e. double-blind).

Each subject will have a unique subject identification code obtained from the interactive voice response system/interactive web response system (IXRS) assigned at the screening visit. The Investigator will keep a record (i.e. the subject screening log) of subjects who entered screening.

Randomization will be performed via the IXRS. At Day 1 (Visit 1, day of vaccination) eligible subjects will be assigned to the respective IMP Lot.

An overview of persons who will be (un)blinded is provided below:

Unblinded:

- DSMB voting members;
- Bio-statistician preparing unblinded analysis for the DSMB.

Blinded:

- Investigators and all other study staff involved in study conduct, safety assessments and IMP handling (i.e. perform preparation of the study vaccine, maintain the drug accountability logs detailing the dates and quantities of IMP administered to each subject);
- Study participant;
- Bio-statistician (except the one involved in DSMB);
- CRA's responsible for monitoring study data, IMP handling and verifying drug accountability (during the study and performing overall drug accountability);

- All laboratory personnel at central laboratories for safety and immunogenicity laboratory assessments;
- All other Sponsor and CRO staff including medical monitor and laboratory personnel at the Sponsor's labs for additional testing procedures.

12.4.1 Blinding Process

Vials are provided to the sites in a blinded manner in order to ensure the blinding of study participants, site staff performing the safety assessments and site staff performing IMP preparation and administration. Identification of the syringe is guaranteed by placing a tear-off label containing Kit number, Subject number, date of injection and operator onto the label.

For further details please refer to the IMP Manual.

12.4.2 Unblinding

The randomization assignment is not to be revealed except in emergency cases in which unblinding is necessary for the clinical management of an SAE. In such events, Investigator must either inform the Sponsor before breaking the blind or immediately after unblinding has been performed.

In case of emergency, the vaccine administered to the subjects can be revealed through the web-response system (IXRS).

12.5 Study Termination - Study Stopping Rules

The study may be paused or prematurely terminated, after consultation with the DSMB, if vaccine-related SAEs or other significant vaccine-related side effects occur. In addition, the Sponsor may stop the entire study for any reason at any time.

If the Sponsor or Investigator decides to terminate the study before it is completed, they will notify each other in writing, stating the reasons for early termination. In terminating the study, the Sponsor and the Investigator will ensure that adequate consideration is given to the protection of the subjects' interests. The Sponsor or Investigator will notify the relevant regulatory authorities or IRB in writing in accordance with local requirements. Documentation will be submitted for filing in the Investigator File and the Trial Master File.

13. SUBJECT SELECTION, WITHDRAWAL AND DISCONTINUATION

Approximately 402 adults of either gender, who satisfy the inclusion and exclusion criteria listed below will be invited to participate in the study.

13.1 Inclusion Criteria

Subjects who meet **ALL** of the following criteria are eligible for this study:

1. Subject is 18 to 45^{vi} years of age on the Day of screening (Visit 0);
2. Subject has an understanding of the study and its procedures, agrees to its provisions, and gives voluntarily written informed consent prior to any study-related procedures;
3. Subject is generally healthy^{vii} as determined by the Investigator's clinical judgement based on medical history, physical examination and screening laboratory tests;
4. If subject is of childbearing potential:
 - a) Subject has practiced an adequate method of contraception (see below) during the 30 days before screening (Visit 0);
 - b) Subject has a negative serum or urine pregnancy test at screening (Visit 0) or Visit 1, respectively;
 - c) Subject agrees to employ adequate birth control measures for the first three months post-vaccination (i.e. until Day 85, Visit 4). This includes one of the following measures:
 - Hormonal contraceptives (e.g. implants, birth control pills, patches);
 - Intrauterine hormone-release systems or intrauterine device;
 - Barrier type of birth control measure (e.g. diaphragms, cervical caps);
 - Vasectomy in the male sex partner \geq 3 months prior to first vaccination.
 - Sexual abstinence;
 - Same sex relationships;
 - Condoms when used in combination with any of the female contraceptive measures outlined above^{viii}.

13.2 Exclusion Criteria

Subjects who meet **ANY** of the following criteria are **NOT** eligible for this study:

^{vi} From the 18th birthday until the last day before the 46th birthday.

^{vii} Subjects are considered **generally healthy** if (1) any chronic illness/condition, e.g. hypertension, type 2 diabetes mellitus, or hyperlipidemia is stable and well-controlled on therapy for the past 6 months, and (2) they do not have a disease that is identified as an exclusion criterion.

^{viii} Condoms are not to be used as a sole means of contraception.

1. Subject has had a CHIKV infection in the past (self-reported), including suspected CHIKV infection; is taking medication or other treatment for unresolved symptoms attributed to a previous CHIKV infection; or has participated in a clinical study involving an investigational CHIKV vaccine;
2. Subject has an acute or recent infection (and who is not symptom-free in the week prior to the Screening Visit (Visit 0);
3. Subject tests positive for human immunodeficiency virus (HIV), hepatitis B surface antigen (HBsAg) or hepatitis C virus (HCV);
4. Subject has received another live virus vaccine within 28 days or inactivated vaccine within 14 days prior to vaccination in this study or plans to receive a vaccine within 28 days or 14 days after vaccination, respectively;
5. Subject has abnormal findings in any required study investigations (including medical history, physical examination, and clinical laboratory) considered clinically relevant by the Investigator which pose a risk for participation in the study based on his/her judgement;
6. Subject has a medical history of or currently has acute or progressive, unstable or uncontrolled clinical conditions (e.g. cardiovascular, respiratory, neurologic, psychiatric, or rheumatologic conditions) that poses a risk for participation in the study, based on Investigators clinical judgement. Examples include individuals with poorly controlled or unstable disease, ongoing suspected or active inflammation, or poor compliance with pharmacologic treatment, or presence of high risk comorbidities (e.g. significant cardiopulmonary disease);
7. Subject has a history of immune-mediated or clinically relevant arthritis/arthralgia;
8. Subject has a history of malignancy in the past 5 years other than squamous cell or basal cell skin cancer. If there has been surgical excision or treatment more than 5 years ago that is considered to have achieved a cure, the subject may be enrolled. A history of hematologic malignancy is a permanent exclusion. Subjects with a history of skin cancer must not be vaccinated at the previous tumor site;
9. Subject has a known or suspected defect of the immune system, such as subjects with congenital or acquired immunodeficiency, including infection with HIV, status post organ transplantation or immuno-suppressive therapy within 4 weeks prior to Visit 1. Immuno-suppressive therapy is defined as administration of chronic (longer than 14 days) prednisone or equivalent ≥ 0.05 mg/kg/day within 4 weeks prior to study entry, radiation therapy or immunosuppressive cytotoxic drugs/ monoclonal antibodies in the previous 3 years; topical and inhaled steroids are allowed.

10. Subject has a history of any vaccine related contraindicating event (e.g., anaphylaxis, allergy to components of the candidate vaccine, other known contraindications);
11. Subject presents with clinical conditions representing a contraindication to intramuscular vaccination and blood draws;
12. Subject is pregnant (positive serum or urine pregnancy test at screening or Visit 1, respectively), has plans to become pregnant during the first three months post-vaccination or lactating at the time of enrollment;
13. Subject has donated blood, blood fractions or plasma within 30 days or received blood-derived products (e.g. plasma) within 90 days prior to vaccination in this study or plans to donate blood or use blood products until Day 180 of the study;
14. Subject has a rash, dermatological condition or tattoos that would, in the opinion of the Investigator, interfere with injection site reaction rating;
15. Subject has a known or suspected problem with alcohol or drug abuse as determined by the Investigator;
16. Subject has any condition that, in the opinion of the Investigator, may compromise the subjects well-being, might interfere with evaluation of study endpoints, or would limit the subject's ability to complete the study;
17. Subject is committed to an institution (by virtue of an order issued either by the judicial or the administrative authorities);
18. Subject has participated in another clinical study involving an investigational medicinal product (IMP) or device within 30 days prior to study enrollment or is scheduled to participate in another clinical study involving an IMP, or device during the course of this study;
19. Subject is a member of the team conducting the study or in a dependent relationship with one of the study team members. Dependent relationships include close relatives (i.e., children, partner/spouse, siblings, parents) as well as employees of the Investigator or site personnel conducting the study.

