13.3 Delay Criteria for Vaccination

Vaccination will be delayed if:

1. Subject has an acute febrile infection within 72 hours prior to vaccination or oral temperature greater than or equal 38.0 °C/ 100.4 °F on the day of vaccination (subject may be rescheduled within the screening visit window until subject has completed 72 hours of no fever);

2. Subject has received antipyretics within 4 hours prior to the scheduled time of vaccination (subject may be rescheduled within the screening visit window).
3. Subject has received any live or inactivated vaccine within 28 days or 14 days prior to vaccination, respectively.

In addition, for a rescheduled vaccination all inclusion and none of the exclusion criteria must be met; in case not all of these criteria are met, the subject will be excluded from the study.

The rescheduled visit should be within the specified time window for the vaccination visit. In case the time window for the rescheduled visit cannot be met, the subject might be invited for a re-screening.

Subjects who have been screen failed under protocol version 2.0 due to the site not receiving the subjects CHIKV-serostatus from the testing laboratory within the 28 day screening window can be asked back for re-screening. All eligibility tests will again be performed with the exception of the CHIKV-serostatus test^{ix}

Moreover, re-screening will not be allowed for subjects who screen fail due to other reasons, such as inclusion/exclusion criteria.

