15.4.1 Part A

Table 15.4-1
Study VLA1553-302 Study Visit Schedule – Part A

VISIT	TIME	ACTION
Visit 0 Screening	Day -28 to 0 (prior to Visit 1)	
 1. Informed consent ^a 2. Inclusion and exclusion criteria (Section 13.1 and 13.2) 3. Demographics ^b 4. Medical history including vaccination history ^c (Section 17.4.1) 5. Prior and concomitant Medications (Section 17.4.2) 6. Physical examination, Hand Stiffness Test ^d and Vital Signs ^e (Section 17.6 and 17.5) 7. Blood draw and urine sample for: 
 a) Serum Pregnancy test ^f b) CHIK Screening ^g c) Safety Sample ^h d) HIV / HBsAg / HCV testing ⁱ
Visit 1 ^j	Day 1	
 1. Inclusion, exclusion and delay criteria (review) (Section 13.1, 13.2 and 13.3) 2. Medical History incl. vaccination history ^c (update) (Section 17.4.1) 3. Concomitant Medications (Section 17.4.2) 4. Symptom-driven physical examination, Hand Stiffness Test ^d and Vital Signs ^e (Section 17.6 and 17.5) 5. Blood draw and urine sample for: 
 a) Urine Pregnancy test ^f b) Baseline Sample ^j c) Immunogenicity ^k d) Viremia ^l e) Safety Sample ^h f) COVID-19 Sample ⁿ 6. Randomization (Section 12.4) 7. VACCINATION (Section 15.3.2)

Table 15.4-1
Study VLA1553-302 Study Visit Schedule – Part A

VISIT	TIME	ACTION
		8. Post-vaccination observation (Section 15.3.3) 9. AE documentation (Section 17.2) 10. Instruct on Subject eDiary ^m (Section 17.3)
Visit 2	Day 8 (+/- 1d)	1. Review Subject eDiary (Section 17.3) 2. AE documentation (Section 17.2) 3. Concomitant medications (17.4.2) 4. Symptom-driven physical examination and Hand Stiffness Test ^d (Section 17.6) 5. Blood draw and urine sample for: a) Immunogenicity ^k b) Viremia ^l c) Safety Sample ^h 6. Instruct on eMemory Aid (Section 17.3)
Visit 3	Day 29 Month 1 (+/- 4d)	1. Review eDiary and eMemory Aid (Section 17.3) 2. AE documentation (Section 17.2) 3. Concomitant Medications (Section 17.4.2) 4. Symptom-driven physical examination and Hand Stiffness Test ^d (Section 17.6) 5. Blood draw and urine sample for: a) Urine Pregnancy test ^f b) Immunogenicity ^k c) Viremia ^l g) Safety Sample ^h h) COVID-19 Sample ⁿ

^a Occurs at enrollment (before Screening).
^b Demographics data include year of birth, age, height, weight, BMI, gender, race and ethnicity.

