17.4.2 Concomitant Medications and Non-Drug Therapies

All medications (including vaccinations) received from 2 weeks prior to study enrollment until completion/termination should be collected from all subjects, and recorded on the appropriate eCRF. In addition to product name (generic name), the dose, indication, route of administration and frequency as well as the start and end date of treatment will be documented.

In addition, medications to treat SAEs will be reported to the Sponsor on SAE Report Forms as described in Section 3. In context of this study, information on non-drug therapies will only be collected in relation to SAEs.

The following medications are **not permitted** if administered within the specified study periods (unless such treatment has to be administered in an emergency situation):

- Any blood products or immunoglobulins during the course of the study;
- Immunosuppressive therapies (e.g. systemic or high dose inhaled [>800 µg/day of beclomethasone dipropionate or equivalent] corticosteroids, radiation treatment or other immunosuppressive or cytotoxic drugs) during the course of the study;
- Prophylactic administration of antipyretics within 4 hours prior to and during the first 72 hours after vaccination;
- Subjects are requested to refrain from donation of blood, blood fractions and plasma within 30 days prior to vaccination and for the entire study duration

For documentary purposes, any of the treatments listed above (including emergency treatment) given within these time periods requires special documentation and is to be documented as a protocol deviation.

The following medications and procedures will **delay** vaccination:

- antipyretics received within 4 hours prior to vaccination.
- any live or inactivated vaccine received within 28 days or 14 days prior to vaccination, respectively.

Usage of any other medications or non-drug therapies is not restricted.

Additionally, medications that are not permitted prior to study enrollment, resulting in exclusion from the study, are reflected in the exclusion criteria in Section 13.2.

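### Criterion 9 allows inhaled steroids at any dose although Section 17.4.2 bars more than 800 µg/day on study, and it counts its 4-week steroid window from two different dates

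*Protocol*

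**What the plan says.** **Entry.** Criterion 9 in Protocol 13.2 excludes subjects with an immune defect, including those who had immunosuppressive therapy in the 4 weeks before Visit 1. It then defines that therapy. The steroid part is more than 14 days of prednisone or equivalent at 0.05 mg/kg/day or above, in the 4 weeks before study entry. The criterion closes with "topical and inhaled steroids are allowed". The synopsis repeats the text, and 18.2 repeats it among the examples of reasons for leaving the per-protocol set.

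**On study.** Section 17.4.2 lists what is not permitted, emergencies apart. One item begins "Immunosuppressive therapies (e.g. systemic or high dose inhaled", puts the inhaled limit at more than 800 µg/day, and continues "beclomethasone dipropionate or equivalent] corticosteroids, radiation treatment or other immunosuppressive or cytotoxic drugs) during the course of the study". Any such treatment "requires special documentation and is to be documented as a protocol deviation".

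**On vaccination day.** The first action for Visit 1 in Table 15.4-1 is "Inclusion, exclusion and delay criteria (review", with references to 13.1, 13.2 and 13.3. The delay criteria in 13.3 are fever or acute febrile infection, antipyretics ("Subject has received antipyretics within 4 hours prior to the scheduled time of vaccination") and recent vaccines. The delay list in 17.4.2 names "antipyretics received within 4 hours prior to vaccination" and recent vaccines. Neither list names corticosteroids.

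**The concern.** The protocol takes two views of the same drug at the same dose. At entry, inhaled steroids are expressly acceptable. On study, a dose above 800 µg/day is immunosuppressive therapy and is not permitted. The case can occur: the footnote on generally healthy subjects admits chronic illness that has been stable and well controlled on therapy for 6 months, so a standing high-dose inhaler does not by itself keep anyone out.

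The second problem is the date from which the 4 weeks run. One criterion uses two anchors that can be four weeks apart, so two sites can reach different answers on the same medication history.

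At stake is mainly the safety of giving a live vaccine. VLA1553 replicates, and 10.5.3 reports short-lived viremia in some Phase 1 subjects, at levels far below natural infection. The documents do not say how much these steroid exposures would add to that risk. Deviations that the entry rules could have prevented are a smaller cost.

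**Working it through.** The plan gives no figure to reproduce here. The check sets the rules side by side and then does the day arithmetic.

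**Step 1. Inhaled steroids**

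| Place | Rule for more than 800 µg/day beclomethasone equivalent |
|---|---|
| 13.2 criterion 9, synopsis, 18.2 | Allowed; no dose stated |
| 13.3 delay criteria | Not mentioned |
| 17.4.2 delay list | Not mentioned |
| 17.4.2 not-permitted list | Immunosuppressive, not permitted during the study; record a deviation |

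A subject on such a dose passes criterion 9 at screening and again at the Visit 1 review, and no delay criterion applies. Under 15.1 a subject is enrolled at consent, so 17.4.2 already applies when the vaccine is given. The deviation exists from the start and lasts as long as the inhaler does.

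**Step 2. The two 4-week windows**

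Criterion 9 does not define study entry. Section 10.4.1 uses the term for the point of serostatus screening, which Table 15.4-1 places at Visit 0, between Day -28 and Day 0. I take it to mean screening.

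Let s be the number of days from study entry to Visit 1, from 0 to 28.

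- Window from Visit 1: the 28 days before Visit 1.
- Window from study entry: from s + 28 days to s days before Visit 1.
- Overlap = 28 - s.

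| s (days) | Overlap (days) |
|---|---|
| 0 | 28 |
| 14 | 14 |
| 28 | 0 |

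Counting Day 0 as a separate day gives 27, 13 and 0 for entry on Day 0, Day -14 and Day -28. The conclusion is the same.

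A course begun after screening lies wholly after the study-entry window. Read literally, it does not meet the definition, even above 0.05 mg/kg/day and still running at Visit 1. It can have lasted more than 14 days by Visit 1 only if s is greater than 14, so this gap needs a screening interval in the upper half of the allowed range.

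**Step 3. What criterion 9 already catches**

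A systemic course begun before entry and still running at Visit 1 has doses in both windows for every s from 0 to 28. If it has lasted more than 14 days at 0.05 mg/kg/day or above, it is excluded under either anchor. The threshold is low: 0.05 × 50 = 2.5 mg/day, 0.05 × 70 = 3.5 mg/day and 0.05 × 100 = 5.0 mg/day for assumed weights of 50, 70 and 100 kg.

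**The case against.** The best reply is that entry rules and on-study rules are meant to be separate. Section 17.4.2 ends by pointing to 13.2 for medication that leads to exclusion before enrollment. Section 20.2 binds the investigator to the protocol, so a duty to record a deviation is no licence to vaccinate. Inclusion 3 and exclusions 5, 6 and 16 also leave room for clinical judgement. All of this stands: the protocol does not approve of vaccinating a subject on high-dose inhaled steroids. It does not remove the conflict. Discretion is a weak safeguard when the specific criterion says that the drug is allowed, and the stated consequence in 17.4.2 is documentation, not withholding the dose.

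On the anchors, the sentence that excludes is tied to Visit 1, zero overlap needs the longest screening interval, and 17.4.2 does not permit immunosuppressive therapy begun after consent. That makes the point small. The ambiguity remains.

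A reader might go further and infer that nothing holds the vaccine for anyone still on corticosteroids at Visit 1. The documents do not support that: step 3 shows that continuing chronic systemic therapy at or above the threshold is excluded and rechecked on the day.

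A reader might also infer a definite conflict for systemic courses of 14 days or less, or below 0.05 mg/kg/day. That depends on the reading. Section 17.4.2 names systemic corticosteroids without a dose or duration. If criterion 9's definition is carried into it, such courses fall under neither rule and there is no conflict.

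**Conclusion.** Two defects hold. The entry criterion has no inhaled dose limit where the on-study rule has one at 800 µg/day, and the 4-week window has two anchors up to 28 days apart. The first rests on the text alone. The second assumes that study entry means screening, which 10.4.1 implies but does not define.

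Severity is minor. The documents do not say how many subjects would be affected; in healthy adults aged 18 to 45 the number is probably small. Lots are assigned at random under blinding, so such subjects should fall evenly across the three arms, and the effect on the GMT ratios is negligible.

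It should not be inferred that the per-protocol review has no rule for these subjects. The list in 18.2 gives examples only, and the Protocol Deviation Guidance Document cited in SAP 9.5 is not among the documents reviewed.

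**What to change.** In criterion 9 and its copies in the synopsis and 18.2:

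- limit the inhaled allowance to 800 µg/day or less of beclomethasone dipropionate or equivalent, the protocol's own limit in 17.4.2;
- count the 4-week steroid window from Visit 1 in both places.

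The cost is wording and a few more exclusions. An exclusion is final for the subject, because 13.3 bars re-screening after failing an exclusion criterion.

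Optional, for the sponsor to judge: add a delay criterion to 13.3, the 17.4.2 delay list and the synopsis for short systemic courses still running at Visit 1. The documents do not settle whether this is needed. A delay would suit better than an exclusion, since 13.3 allows rescheduling and adds: "In case the time window for the rescheduled visit cannot be met, the subject might be invited for a re-screening". A course of at most 14 days would delay vaccination by at most 14 days. That fits the 28-day screening window if Visit 1 was planned within 14 days of screening (14 + 14 = 28). The sponsor would also have to decide whether vaccination may follow on the first drug-free day or only after a washout.
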